5.1.3 Exploratory Efficacy Endpoints

5.1.3.1 Percent Change in HCe Dose at Week 24

Exploratory Efficacy Endpoint 3.1 evaluates the effect of randomized treatment in reducing GC HCe dose in classic CAH subjects at Week 24 in mean percentage terms. This analysis will be achieved by examination of the change in daily GC HCe dose from baseline (Day 1) to post baseline visits on the log scale. Results will be back transformed to present the outcome as a percentage change.

5.1.3.2 Cumulative HCe Dose at Week 24

Exploratory Efficacy Endpoint 3.2 evaluates the effect of randomized treatment in reducing the cumulative HCe dose (total exposure in HCe mg) in classic CAH subjects over 24 Weeks. The endpoint is the cumulative GC dose in HCe from baseline (Day 1) at Week 24. Similar to endpoint 3.1, the endpoint will be analyzed on the log scale.

5.1.3.3 Change in HOMA-IR at Weeks 24 and 52

Exploratory Efficacy Endpoints 3.3 and 3.4 evaluate the effect of randomized treatment in improving HOMA-IR in classic CAH subjects at Weeks 24 and 52. The associated endpoints are the change in fasting HOMA-IR from baseline (Day 1) to Week 24 and Week 52.

5.1.3.4 Improving Cardiovascular Risk Factors at Week 52

Exploratory Efficacy Endpoint 3.5 evaluates the effect of randomized treatment in reducing CV risk factors in classic CAH subjects at Week 52. The endpoint is similar to Secondary Efficacy Endpoint 2.3, being the proportion of subjects who had improvement in at least one CV risk factor at Week 52. Only subjects CV risk factors at baseline will be included in the endpoint analysis.

5.1.3.5 GC use while maintaining androgen control at Week 52

Exploratory Efficacy Endpoints 3.6 and 3.7 are similar to the Secondary Efficacy Endpoints 2.1 and 2.2, but now assessed at 52 weeks. Secondary Efficacy Endpoints 3.6 is the response to randomized treatment in terms of reducing GC to $\leq 11\text{mg mg/m}^2/\text{day}$ in HCe while maintaining

androgen control, defined as A4 levels at approximately baseline ($\leq 1.2x$ baseline) or within normal limits (\leq ULN) at Week 52 in subjects with CAH.

Exploratory Efficacy Endpoint 3.7 is similar to 3.6 but evaluated in those subjects with baseline GC ≤ 35 mg/m²/day in HCe.

5.1.3.6 Quality of Life at Week 24 and Week 52

Exploratory Efficacy Endpoints 3.8 and 3.9 evaluate the effect of randomized treatment in improving the quality of life as quantified by the Short Form-36 total score in classic CAH subjects at Weeks 24 and 52. The endpoints are the change in the SF-36(8 subscales using the population-based normalized values, as well as PCS and MCS population-based normalized values) from baseline (Day 1) at Week 24 and Week 52.

5.1.3.7 Change in BMI at Week 24 and Week 52

Exploratory Efficacy Endpoints 3.10 and 3.11 evaluate the effect of randomized treatment on BMI in classic CAH subjects. The Secondary Efficacy Endpoint is the percent change in BMI from baseline (Day 1) to Week 24 and Week 52.

5.1.3.8 Waist Circumference at Week 24 and Week 52

Exploratory Efficacy Endpoints 3.12 and 3.13 evaluate the effect of randomized treatment in decreasing waist circumference in classic CAH subjects at Weeks 24 and 52. The endpoints are the change in waist circumference from baseline (Day 1) to Week 24 and Week 52.

5.1.3.9 Change in Body Composition at Week 24 and Week 52

Exploratory Efficacy Endpoints 3.14 and 3.15 evaluate the effect of randomized treatment in improving percent total fat mass and total percent lean mass in classic CAH subjects at Week 24 and Week 52. The associated endpoints are the change in percent total fat mass and total percent lean mass from baseline (Day 1) to Week 24 and Week 52.

5.1.3.10 Change in Bone Mineral Density at Week 24 and Week 52

Exploratory Efficacy Endpoint 3.16 evaluates the effect of randomized treatment in improving BMD in classic CAH subjects at Week 52. The endpoint is the change in total BMD from baseline (Day 1) to Week 24 and to Week 52.

5.1.3.11 Change in TART volume at Week 24 and Week 52

Change in TART volume is assessed by Exploratory Efficacy Endpoints 3.17 and 3.18. These endpoints evaluate the effect of randomized treatment in reducing TART volume in classic CAH subjects at Week 24 and Week 52. Both endpoints will only include those subjects whom had TART(s) at baseline. The associated endpoints are thus (i) the change in total TART volume from baseline (Day 1) to Week 24 in subjects whom had TART(s) at baseline and (ii) the change in total TART volume from baseline (Day 1) to Week 52 in subjects whom had TART(s) at baseline.

5.1.3.12 GC use while maintaining androgen control at Week 24 and Week 52 in subjects with CAH

To further evaluate the effect of randomized treatment in reducing GC use while maintaining androgen control, defined as normal A4 levels at Week 24 in subjects with CAH, Exploratory Efficacy Endpoints 3.19 and 3.20 evaluate response to randomized treatment in terms of the proportion of subjects with at least a 5 mg/day HCe reduction from baseline (Day 1) in GC dose and $A4 \leq 1.2 \times \text{baseline}$ or $A4 \leq \text{ULN}$ at (i) Week 24 and (ii) Week 52.

5.2 Safety Objective

The safety objective of the study is to evaluate the safety of tildacerfont in classic CAH patients using safety assessments described in [Section 4.3.1.6](#).

6 SAMPLE SIZE AND POWER

The original sample size calculation was based the binary endpoint of percent of subjects with a 5 mg/day HCe reduction from baseline in GC dose at Week 24 with $A4 \leq \text{ULN}$. Assuming a

placebo group response of 30%, N = 45 subjects per group would provide at least 90% power to detect a between group relative difference of 33% at the 0.05 two-sided type I error rate.

Additionally, it was computed that a sample size of N=45 subjects per group would provide at least 90% power to detect a mean change in daily GC dose from baseline and placebo of 7.25 mg/day in HCe, assuming a standard deviation (SD) of 10.5 mg/day HCe and the two-sided type I error is 0.05. Examination of group blinded data, provides a conservative SD estimate of 6.9 mg/day. On this basis, a sample size of N=40 subjects per group provides at least 90% power to detect a mean change in daily GC dose from baseline and placebo of 5 mg/day in HCe with a two-sided type I error of 0.05.

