Efficacy endpoints after 52 weeks of tildacerfont treatment will be evaluated using the following hypothesis-testing schema: The Week 52 value will be compared with the baseline value. The null hypothesis will be that there is no difference between the Week 52 and baseline values. The alternative hypothesis will be that there is a difference.

Sample Size

A sample size of N=45 subjects per group will provide at least 90% power to detect a between group difference in the proportion of subjects with at least a 5 mg/day HCe reduction from baseline in GC dose at Week 24 with A4 \leq ULN of at least 33% assuming the placebo group has a response of 30% and the two-sided type I error is 0.05.

Analysis Populations

- The Intent-to-Treat (ITT) Population will include all randomized subjects.
- The modified ITT (mITT) Population will include all randomized subjects who receive at least 1 dose of study drug (tildacerfont or placebo).

- The Per Protocol (PP) Population will include all randomized subjects who have no major protocol violations that would affect the analysis of efficacy data.
- The Safety Population will include all subjects who receive at least 1 dose of study drug (tildacerfont or placebo).
- The Pharmacokinetics (PK) Population will include all subjects who receive at least 1 dose of tildacerfont and have at least 1 evaluable PK sample.

Refer to [Section 9.3](#) for further information on analysis populations.

General Statistical Considerations

Unless otherwise specified, continuous adrenal biomarkers (A4, 17-OHP, ACTH) will be summarized using a 11-point descriptive statistics (i.e., n, mean, standard deviation [SD], median, 25% quartile [Q1], 75% quartile [Q3], minimum, maximum, geometric mean, geometric coefficient of variance [CV%], 95% confidence interval [CI] for geometric mean [including geometric mean ratio and its 95% CI]). Continuous data aside from (A4, 17-OHP and ACTH) will be summarized using an 8-point descriptive summary (n, mean, SD, median, Q1, Q3, minimum, and maximum). Categorical data will be summarized using the frequency of events and percentage of total events.

For missing data, a retrieved dropout approach will be used in which missing endpoint data for subjects who discontinued early will be imputed using data collected from subjects after discontinuation of study drug.

Efficacy Analyses

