9.2 Sample Size Determination

A sample size of N=45 subjects per group will provide at least 90% power to detect a between group difference in the proportion of subjects with at least a 5 mg/day HCe reduction from baseline in GC dose at Week 24 with A4 \leq ULN of at least 33%, assuming the placebo group has a response of 30% and the two-sided type I error is 0.05.

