4 STUDY DESIGN

This is a multi-center, randomized, double-blind, placebo-controlled, clinical study to evaluate the efficacy and safety of tildacerfont in reducing supraphysiologic glucocorticoid (GC) use in

adult subjects with classic CAH who have androstenedione (A4) ≤ 2.5 x upper limit of normal (ULN) and are on supraphysiologic doses of GC therapy (≥ 30 mg/day and ≤ 60 mg/day in hydrocortisone equivalents [HCe]) at baseline. This study consists of the following periods:

- ≤ 45 -day Screening Period will confirm subject eligibility
- Week -12 to either Week -6 or Week -2 Day -1 [± 3 days] GC Conversion Period, if applicable
- 76-week, 2-part Treatment Period
 - 24-week Placebo-Controlled Treatment Period
 - 52-week Open-Label Period
- 240-week, optional Open-Label Extension Period
- 30-day Follow-up Period

Per sample size calculations, a total of 90 adult subjects with classic CAH were planned to be randomized into the 76-week Treatment Period. Subjects on dexamethasone at the initial Screening Visit who agree to convert to a non-dexamethasone regimen will enter the GC Conversion Period for conversion to and stabilization on a non-dexamethasone regimen as determined by their physician. Subjects enrolled under protocol amendment \leq version 6 could also complete the GC Conversion Period to convert and stabilize to Sponsor supplied GC regimens, hydrocortisone (3 times daily) TID or prednisolone (twice daily) BID, if the subject was not on one of these regimens at screening. Subjects enrolled under and after protocol amendment 7, who are not on dexamethasone at screening, will continue on their current GC regimen at screening without the need for conversion to a standardized GC regimen prior to entering the treatment period. Permitted GC regimens include either monotherapy or combination therapy of the following GC types, hydrocortisone, hydrocortisone acetate, prednisone, prednisolone, or methylprednisolone.

Upon completion of the Screening period and GC Conversion Period, if applicable, subjects who continue to meet eligibility criteria will enter the randomized, Double-Blind, Placebo-Controlled Treatment Period. Subjects will be randomized in a 1:1 ratio to receive either tildacerfont at a dose of 200 mg QD (once a day) or matching placebo for the 24-week, double-blind part of the study. During this part of the study, a subject's daily GC regimen may be adjusted

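### SAP section 6 claims at least 90% power for a relative difference of 33% on a 30% placebo response; as worded, 45 per group gives about 16% to 17%, and the word *relative* is the likely error

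*SAP*

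**What the plan says.** SAP section 6 opens with the calculation for the binary endpoint: a reduction of 5 mg/day HCe in GC dose at Week 24 with A4 at or below the ULN. It assumes a "placebo group response of 30" percent and says that "N = 45 subjects per group would provide at least 90% power to detect a between group relative difference of 33" percent, "at the 0.05 two-sided type I error rate". SAP section 4 ties the planned total to this kind of calculation: "Per sample size calculations, a total of 90 adult subjects with classic CAH were planned to be randomized".

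Protocol 9.2 describes the same calculation as "at least 90% power to detect a between group difference in the proportion of subjects" meeting the responder criterion. The synopsis completes it with a difference "of at least 33% assuming the placebo group has a response of 30% and the two-sided type I error is 0.05". Sample size per group, power, placebo rate, alpha and the figure of 33% are the same in both documents. Only the SAP calls the difference relative. The protocol says neither that it is absolute nor what response is expected on tildacerfont.

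SAP 6 presents the binary calculation as the original one. SAP 12.3.1 explains that the primary endpoint has since become the continuous change in GC dose. SAP 6 then gives two further calculations for that endpoint: 7.25 mg/day with SD 10.5 and 45 per group, and 5 mg/day with SD 6.9 and 40 per group.

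**The concern.** Every input needed to check the claim is in one SAP sentence, and the inputs do not fit together. A third more responders than 30% is a gain of about 10 percentage points, and 45 per group is far too few to detect that with 90% power. The SAP also departs from the protocol's wording for what is plainly the same calculation.

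A reader who takes the SAP at its word would believe that the trial was sized to detect a responder difference of about 10 points, when it was sized for one about three times as large. That matters for anyone interpreting the responder analyses that remain. The closest is exploratory endpoint 3.19, which keeps the 5 mg/day reduction with a looser A4 criterion. It does not bear on the power of the current primary analysis.

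**Working it through.** **Inputs.** Placebo rate p1 = 0.30, n = 45 per group, two-sided alpha 0.05 (z = 1.960) and stated power of at least 90%, all from SAP 6 and the same in Protocol 9.2. Allocation is 1:1 (SAP 4.1).

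**Formulas.** Let d = p2 − p1, p̄ = (p1 + p2)/2, SE0 = √[2p̄(1 − p̄)/n] and SE1 = √[(p1(1 − p1) + p2(1 − p2))/n].
- Pooled power: Φ[(d − 1.960·SE0)/SE1]
- Unpooled power: Φ[d/SE1 − 1.960]

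**Step 1: the reading that reproduces the claim.** Take 33% as percentage points, so p2 = 0.63 and d = 0.33.
- SE0 = √(0.49755/45) = 0.1052 and SE1 = √(0.4431/45) = 0.0992.
- Pooled: Φ[(0.33 − 0.2061)/0.0992] = Φ(1.25) = 89.4%.
- Unpooled: Φ(3.326 − 1.960) = Φ(1.37) = 91.4%.
- Per-group size for 90%: 46 pooled, 43 unpooled.
- In relative terms this difference is 0.33/0.30 = 110%.

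**Step 2: the SAP as worded.** A relative difference of 33% gives p2 = 0.30 × 1.33 = 0.399 and d = 0.099.
- SE0 = √(0.4547/45) = 0.1005 and SE1 = √(0.4498/45) = 0.1000.
- Pooled: Φ[(0.099 − 0.1970)/0.1000] = Φ(−0.98) = 16.3%.
- Unpooled: Φ(0.990 − 1.960) = Φ(−0.97) = 16.6%.
- Enumerating all outcomes for the uncorrected score (Pearson chi-square) test: 17.1%.
- Per-group size for 90% (pooled): [1.960·√0.4547 + 1.282·√0.4498]²/0.099² ≈ 4.757/0.009801 = 485.4, so 486 per group and 972 in total.

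**Step 3: other meanings of *relative*.** None gets near 90%.

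| Reading | p2 | Power, pooled / unpooled |
|---|---|---|
| Difference is 33% of the active rate | 0.30/0.67 = 0.448 | 30.2% / 31.1% |
| Non-response cut by 33% | 1 − 0.70 × 0.67 = 0.531 | 60.7% / 62.8% |
| Odds ratio of 1.33 | 0.363 | 9.2% / 9.3% |
| Absolute, 33 points | 0.63 | 89.4% / 91.4% |

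**Step 4: what 45 per group can detect at 90% power.** From 30%, the detectable difference is 33.3 points (pooled) or 32.2 points (unpooled). These are relative differences of 111% and 107%.

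**Step 5: the current primary endpoint.** With z = difference/(SD·√(2/n)):
- 7.25/(10.5·√(2/45)) = 3.275, which gives 90.6% by the normal approximation and 90.0% by noncentral t.
- 5/(6.9·√(2/40)) = 3.241, which gives 90.0% by the normal approximation and 89.3% by noncentral t.

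Both agree with the SAP's figure to within a point.

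**The case against.** The strongest reply is that this is a slip of wording whose meaning can be recovered. The protocol gives the same numbers as a difference in proportions, which is naturally read as percentage points and returns about 90%. The SAP may have used *relative* loosely, to mean relative to placebo. No document plans for 30% against 39.9%, so quoting 16% power could leave the false impression of an underpowered trial. SAP 6 itself treats the calculation as historical, and no analysis or decision depends on it. The clause in SAP section 3 that makes the SAP prevail over the protocol concerns planned analyses, and does not clearly reach a sample-size rationale.

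Much of this stands, and it is why the point is minor. It does not rescue the sentence: a stated effect size of 30% to 39.9% and a stated power of 90% are incompatible with 45 per group, and the gap is far too wide to come from the choice of formula or from rounding.

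Two further remarks are fair. First, 30% against 63% is an inference, because the protocol states neither the word absolute nor the 63%. Second, even on that reading, at least 90% depends on the method. Power is 91.4% unpooled and 89.4% pooled, 88.6% for the uncorrected score test by enumeration, and 83.9% for Fisher's exact test. SAP 12.5.1.1 uses an exact score test for the binary secondary endpoints, with Fisher's test as the fallback, so the unpooled figure is the favourable one.

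**Conclusion.** The SAP sentence is wrong as written. At two-sided 0.05 with 45 per group, a 33% relative difference on a 30% placebo response has 16.3% to 17.1% power by the pooled, unpooled and score-test calculations, not 90%. Of the readings tried, only an absolute difference of 33 points comes near the stated power. The likely fault is therefore the word *relative* and not the sample size. That diagnosis assumes that the SAP and the protocol describe one and the same calculation, as their shared inputs indicate.

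Severity is minor. The calculation belongs to a binary endpoint that is no longer primary, and the power given for the continuous primary endpoint reproduces at about 90%. Nothing here shows that the current primary analysis is underpowered.

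**What to change.** Ask the sponsor to confirm the effect that was intended. If it is 30% against 63%, replace the relative difference of 33% in SAP 6 with an absolute difference of 33 percentage points (30% vs 63%). In the same sentence, name the formula or test assumed, because the 90% is met with unpooled variance (91.4%) and narrowly missed with pooled variance (89.4%).

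The cost is one phrase in the SAP. The sample size, the analyses and the number of patients do not change. Protocol 9.2 and the synopsis are less explicit than they could be, but they do not contradict their own power figure, so no amendment is needed.

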7 ANALYSIS SETS

7.1 Intent-To-Treat Analysis Set

The Intent-To-Treat (ITT) Analysis Set will include all randomized subjects (based on the RTSM system as described in Section 4.1) regardless of Treatment Period eligibility or completion. The ITT Analysis Set will be the basis for demographics, baseline characteristics, and efficacy.

7.2 Modified Intent-To-Treat Analysis Set

The modified ITT (mITT) Analysis Set will include all randomized subjects who receive at least 1 dose of study drug (tildacerfont or placebo) and have a baseline A4 assessment. The mITT population will be used for supportive analyses of the Primary and Secondary Efficacy Endpoints if it differs from the ITT population.

7.3 Per-Protocol Analysis Set

The Per-Protocol (PP) Analysis Set for each part of the Treatment Period will include all eligible subjects who have no major protocol deviations that would affect the analysis of efficacy data, defined prior to the database lock as the following:

- Subject did not meet efficacy-based inclusion criteria (hormone levels, GC regimen)

- Subject met efficacy-based exclusion criteria (inadequate adherence to GC regimen, night-shift worker)
- Subject's adherence to study drug or the subject-specific GC regimen, determined by pill count and diary data compliance, was < 80% over the Treatment Period
- Subjects having laboratory data specifically hormone levels during stress dosing periods instead of waiting 5 days per protocol.

The PP population will be used for supportive analyses of the Primary and Secondary Efficacy Endpoints only.

7.4 Safety Analysis Set

The Safety (SAF) Analysis Set is defined as all subjects who received at least one dose of study drug (placebo or tildacerfont). The safety analysis set, which will be based on the actual treatment received, will be used for evaluation of general medical history, study drug exposure, concomitant medication, and safety. Placebo-treated subjects who received any amount of tildacerfont during the Open-Label Period will be assigned to the tildacerfont treatment group from the time when tildacerfont was received.

7.5 DXA Analysis Set

The dual-energy X-ray absorptiometry (DXA) analysis set is defined as all ITT subjects who have a baseline and post-baseline evaluable scan. The DXA analysis set will be used to analyze bone mineral density efficacy assessments.

8 GENERAL CONSIDERATIONS

Data summarization and presentation conventions are documented in the Appendix A for mock-shells. All analyses and summaries will be produced using SAS® version 9.4 or higher.

8.1 Presentation of Summary Statistics

For most summary statistics, data will be displayed in tabular format. Unless otherwise specified, continuous adrenal biomarkers (A4, 17-OHP, ACTH) will be summarized using a 11-point descriptive statistics (i.e., n, mean, standard deviation [SD], median, 25% quartile [Q1], 75% quartile [Q3], minimum, maximum, geometric mean, geometric coefficient of variance [CV%],

95% confidence interval [CI] for geometric mean [including geometric mean ratio and its 95% CI]. All other continuous variables will be summarized using an 8-point descriptive summary (n, mean, SD, median, Q1, Q3, minimum, and maximum). The same number of decimal places as in the observed value will be presented when reporting minimum and maximum; 1 additional decimal place than in the observed value will be presented when reporting mean, median, Q1, Q3, geometric mean, 95% CI; 2 additional decimal places than in the observed value will be presented when reporting SD. Geometric CV% will be reported to one decimal place.

All categorical/qualitative data will be presented using the frequency of events and percentages. All percentages will be presented to 1 decimal place, unless otherwise specified. Percentages equal to 100 will be presented as 100% and percentages will not be presented for zero frequencies. Where individual variable values are missing, categorical data will be summarized based on reduced denominators (i.e., only subjects with available data will be included in the denominators).

For summaries of AEs and concomitant medications (CMs), the percentages will be based on the number of subjects who received study drug.

8.2 Presentation of p-values

Results of statistical analyses will be reported using summary tables, listings, and figures (TLFs). The ICH of Technical Requirements for Pharmaceuticals for Human Use numbering convention will be used for all TLFs. The following conventions will be followed:

Unless otherwise noted, all statistical testing will be two-sided and will be performed at the 0.05 significance level. Tests will be declared statistically significant if the calculated p-value is < 0.05 , unless otherwise specified. P-values will be reported with 4 significant digits except when reporting p-values less than 0.001, reported as < 0.001 .

8.3 Definitions and Derived Variables

8.3.1 Screened and Enrolled Subjects

8.3.1.1 Screened Subjects

Subjects who signed an informed consent form are considered Screened Subjects

